8.6 Derived and Computed Variables

Demographics

Age, if not already provided, will be calculated in years using the following formula:

$$\text{Age (years)} = (\text{Date of Visit 1} - \text{Date of Birth} + 1) / 365.25, \text{ round to smallest integer}$$

Body Mass Index (BMI, kg/m²) will be calculated using the following formula:

$$\text{BMI} = \text{Weight (kg)} / \text{Height}^2 \text{ (m}^2\text{)}$$

Immunogenicity

Values below the limit of quantification (recorded as "< LQ") will be set to half that limit (LQ/2).

Titer greater or equal to a given threshold is defined as binary variable for non-missing values as:

= 1, if the titer is superior or equal to the given threshold

= 0, otherwise

HI antibody titer $\geq 1:40$ is defined as binary variable for subjects with non-missing values as:

= 1, if achieving a HI antibody titer $\geq 1:40$

= 0, otherwise

Seroconversion is defined as binary variable for subjects with non-missing values pre-vaccination and post-vaccination as:

= 1, if seroconverted (defined as the percentage of subjects with either a pre-vaccination HI titer $< 1:10$ and a post-vaccination HI titer $\geq 1:40$ or a pre-vaccination HI titer $\geq 1:10$ and a minimum 4-fold rise in post-vaccination HI antibody titer)

= 0, otherwise

Geometric Mean Titer/Concentration

The GMT will be calculated using the following formula:

$$10^{\left\{ \frac{\sum_{i=1}^n \log_{10}(t_i)}{n} \right\}}$$

where t_1, t_2, \dots, t_n are n observed immunogenicity titers/concentrations.

Geometric Mean Ratio

Geometric mean ratios (GMRs) measure the changes in immunogenicity titers/concentrations *within* subjects.

The GMR will be calculated using the following formula:

$$10^{\left\{ \frac{\sum_{i=1}^n \log_{10}\left(\frac{v_{ij}}{v_{ik}}\right)}{n} \right\}} = 10^{\left\{ \frac{\sum_{i=1}^n \log_{10}(v_{ij}) - \log_{10}(v_{ik})}{n} \right\}}$$

where, for n subjects, v_{ij} and v_{ik} are observed immunogenicity titers/concentrations for subject i at time-points j and k , $j \neq k$.

Duration in the Study

Duration of study per subject based on last phone call defined as Day 181 (for “previously vaccinated” subjects) or Day 209 (for “not previously vaccinated” subjects), or until the end of influenza season, whichever is longer.

Duration in the study is defined in days as:

Last visit date (last visit)^a – Enrollment date (visit 1) + 1

^aor premature discontinuation date (in case of withdrawal from the study)

The duration is missing if one of the dates is missing or incomplete.

Solicited Adverse Events

For details, see [Section 13.2](#).

Unsolicited Adverse Events

All adverse events will be characterized according to the date of occurrence related to the vaccination phase as follows:

- **Emergence before vaccination phase:** start date before the first date of injection of study vaccine.
- **Emergence during vaccination phase:** start date on or after the first date of injection of study vaccine or, adverse event increase in severity including to “serious” adverse event.

If the start date is equal to the first date of injection then a “timing” variable (“On injection day, before injection” / “On injection day, after injection”) will be used to define whether the adverse event occurred before or after the injection.

If there are several vaccinations, the adverse event will be associated with the most recent vaccination.

If an adverse event start date is missing or unknown, the adverse event will be considered as emergent.

When start and/or end dates of an adverse event are only partially known, adverse events will be categorized as emergent before, during, or after vaccination phase using the following rules:

- If the partial end date is before (<) the first study vaccination (i.e., year or year & month is/are before the first study vaccination year or year & month) then the adverse event is emergent before vaccination phase.
- If the partial start date is equal or after (\geq) the first study vaccination (i.e., year or year & month is/are after or the same as the first study injection year or year & month) then the adverse event is emergent during vaccination phase.

The **maximum event severity** is the greatest severity associated with a preferred term for a reported adverse event according to the following order: Mild < Moderate < Severe. Unknown/ Missing severity is considered as severe (except for the definition of emergence).

Multiple AEs with the same PT for the same subject are counted only once.

Vaccination-related Adverse Events are those for which the cause has been evaluated by the investigator, and recorded either as possibly related, probably related or unknown/missing.

Safety Laboratory Data

Not applicable.

Pre-study, Concomitant and Post-Study Medications

A **pre-study medication** is a medication used only before the first study vaccination (i.e. medication end date < first study vaccination date).

A **post-study medication** is a medication used only after study termination (i.e. medication start date > study termination date). This will not be collected in the clinical database and will not be reported in the CSR.

All other medications are **concomitant**.

When start and/or end dates of a medication intake are missing, the medication is considered as concomitant with the study vaccination schedule.

If the first study vaccination date is missing then the medication is considered as concomitant with the study vaccination schedule, provided that the study vaccine was administered to the subject.

8.7 Analysis Software

All analyses will be performed using SAS[®] Software version 9.2 or higher.

8.8 Data Transformation

Distributions of antibodies are generally skewed to the right ([Nauta, 2010](#)). Therefore, prior to any statistical analysis that assumes normally distributed observations, antibody titers or concentrations will be log₁₀-transformed. GMTs and their 95% CIs will be computed by exponentiating (base 10) the least squares means and associated 95% CIs of the log₁₀ titers.

9. STUDY SUBJECTS

9.1 Disposition of Subjects and Withdrawals

All enrolled subjects will be accounted for in this study and displayed along with the frequencies and percentages of subjects enrolled, vaccinated, completed and withdrawn (including reason for withdrawal) for the Enrolled Set. The frequencies and percentages of subjects with CSR reportable PDs will be presented for the FAS (Efficacy and Immunogenicity).

The time the subjects are under observation will be summarized by vaccine and overall using summary statistics (mean, standard deviation, minimum, median, maximum) and compared between treatment arms.

The numbers and percentages of subjects in each analysis set, study withdrawals, subgroups, and major protocol deviations will also be presented.

10. DEMOGRAPHICS AND OTHER BASELINE CHARACTERISTICS

10.1 Demographics

Age, height, weight, body mass index will be summarized by reporting the mean, standard deviation, median, minimum and maximum, and will be calculated by vaccine group and overall. They will be also reported by age groups.

The frequencies and percentages of subjects by country, sex, ethnic origin, race and age, meeting or not-meeting of protocol entrance criteria and “previously vaccination” status will be presented by vaccine group and overall, stratified by age categories and Season and then by Season and country. Demographic data will be tabulated for the Enrolled, FAS (Efficacy, Immunogenicity HI), PPS (Efficacy) and Safety sets.

10.2 Medical History

The frequencies and percentages of subjects with medical history and by Medical Dictionary for Regulatory Activities (MedDRA) system organ class (SOC) and preferred term (PT) will be presented overall and by vaccine group and for the different age categories, by Season, and for “previously vaccination” status. Medical history data will be tabulated for the Enrolled Set, FAS (Efficacy) and Safety Sets.

11. EFFICACY ANALYSIS

11.1 Primary Efficacy Objectives Analysis

Efficacy will be evaluated in all subjects in relation to cases occurring >14 days after last vaccination and until the end of study or the end of the influenza season, whichever is longer, using the following null (H_0) and alternative (H_1) hypotheses:

$$H_0: 1 - HR = VE \leq 0.2 \quad \text{versus} \quad H_1: 1 - HR = VE > 0.2,$$

where HR is a hazard ratio of QIVc versus non-influenza comparator and VE is vaccine efficacy. The primary objective will be achieved if the lower limit of the two-sided confidence interval of VE estimate, with at least 95% coverage in a multiple sequential hypothesis testing, exceeds 0.2 in subjects ≥ 2 years to <18 years of age.

The co-primary objective will be achieved if the lower limit of the two-sided confidence interval of VE estimate, with at least 95% coverage in a multiple sequential hypothesis testing, exceeds 0.3 in subjects ≥ 3 years to <18 years of age.

The co-primary objective will only be demonstrated in case of successful demonstration of the primary efficacy objective (i.e. in hierarchical testing procedure, only after demonstration of absolute vaccine efficacy of QIVc in subjects ≥ 2 years to <18 years of age).

In case an interim analysis will be performed the 95% CI will be adjusted accordingly. If an interim analysis is performed and the trial doesn't stop, then all the subsequent analysis will be tested at a reduced alpha level, i.e. what's left from the interim analysis. The confidence interval will be higher than 95% instead of 95% for the final analysis.

(Co-)Primary vaccine efficacy analyses will be based on the Efficacy FAS, and repeated on the Efficacy PPS.

For each of the age groups (≥ 2 to <18 and ≥ 3 to <18 years), the HR² and the related 95% CI of HR, for onset of first RT-PCR or culture confirmed influenza will be estimated by a proportional hazards regression model with treatment effect as a fixed effect and stratifying covariates as random effect:

$h_i(t|X) = h_0(t) \exp(\beta^T X + b^T Z)$, with t denoting time to the influenza, β is the effect of treatment group indicated by X , b is random effect (assumed as a multivariable random gaussian variable with zero mean and diagonal covariance matrix), Z is random effect covariate (reflecting randomization strata, see [Section 8.1](#) for further discussion of the covariates utilized).

² Formula: $VE=1-HR$

Subjects that did not experience ILI during observation period and subjects that dropped out from the study during observational period will be censored (right-censoring). The estimate of the hazard ratio, the respective estimate for absolute VE and the pertaining two-sided CIs will be calculated based on this model. If the study continues over several seasons, estimates will be also adjusted for the factor season (s). In case of one or two (interim) analyses, confidence levels at each stage will be adjusted, as discussed in section 14.1, to provide 95% overall coverage.

For each of the age groups (≥ 2 to <18 and ≥ 3 to <18 years), estimates for hazard ratio in Cox Proportional hazard (PH) model will be calculated using Maximum Likelihood (ML) method. In case of problems with convergence (algorithm does not converge or converges to infinite estimates) penalized ML approach will be used (Heinze and Schemper).

Vaccine efficacy $VE = 1 - HR$, that is, $1 - \exp(\hat{\beta})$

with $\hat{\beta}$ with $100(1 - \alpha)$ percent confidence interval as:

$[1 - \exp(+Z(s.e.(\hat{\beta}))); 1 - \exp(\hat{\beta} - Z(s.e.(\hat{\beta})))]$. Z is the $100(1 - \alpha)$ percent point of the standard normal distribution, and s.e. denotes the standard error of β

Subjects that did not experience ILI during observation period and subjects that dropped out from the study during observational period will be censored (right-censoring).

The hazard ratio is the predicted ratio of cases of Influenza A and or B disease in subjects receiving QIVc and non-influenza vaccine comparator within each of the strata of interest. The term β_g is the estimate of treatment effect (or regression coefficient) between QIVc and non-influenza vaccine comparator within each of the stratum.

The estimate of the hazard ratio, the respective estimate for absolute VE and pertaining two-sided 95% CIs will be calculated based on this model. If the study continues over several seasons, estimates will be also adjusted for the factor season (s). Factor country might be added to the model if appropriate. In case of more than one interim analysis confidence level for the estimates at the final stage will be adjusted.

Primary analysis will take into account only first ILI episode for a subject.

In addition VE estimate estimated from Cox proportional model (for each of the age strata (≥ 2 to <18 and ≥ 3 to <18 years) a simple unadjusted estimate of VE will be also presented as $1 - \pi_{QIVc} / \pi_{Comp}$ along with 95% exact unconditional confidence interval; where π_{QIVc} and π_{Comp} will be attack rates for each group estimated as a binomial variable.

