
enhance the understanding of immune responses to QIVc vaccination. This study is a regulatory requirement to support the licensure of QIVc for use in children ≥ 4 years of age in the United States (US). Children ≥ 2 years of age are enrolled in this study to further evaluate QIVc in a broader age range and to support submissions in various global regions.
 
The purpose of this study is to demonstrate the efficacy (absolute vaccine efficacy [aVE]), immunogenicity, and safety and tolerability of QIVc compared to non-influenza comparator vaccine in subjects ≥ 2 years to < 18 years of age. If there is more than one season, data from all seasons will be combined.
		

Efficacy Objectives:
 
Efficacy will be evaluated in all subjects in relation to cases occurring > 14 days after last vaccination and until the end of the influenza season.
 
Primary Efficacy Objective(s):
 
To demonstrate absolute vaccine efficacy of QIVc versus a non-influenza comparator determined by first occurrence RT-PCR or culture confirmed influenza, due to any influenza Type A and B strain in subjects ≥ 2 years to < 18 years of age.
 
In case of successful demonstration (see section 8.2) of the primary efficacy objective:
 
Co-Primary Efficacy Objective(s):
 
To demonstrate absolute vaccine efficacy of QIVc versus a non-influenza comparator determined by first occurrence RT-PCR or culture confirmed influenza, due to any influenza Type A and B strain in subjects ≥ 3 years to < 18 years of age.
		

Name of Sponsor: Seqirus UK Ltd	Protocol number: V130_12	Generic name of study vaccine(s): Cell-Based Quadrivalent Subunit Influenza Virus Vaccine (QIVc) Meningococcal (Groups A, C, Y, W-135) Conjugate Vaccine (Men ACWY)

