Name of Sponsor: Seqirus UK Ltd	Protocol number: V130_12	Generic name of study vaccine(s): Cell-Based Quadrivalent Subunit Influenza Virus Vaccine (QIVc) Meningococcal (Groups A, C, Y, W-135) Conjugate Vaccine (Men ACWY)

Culture positive samples will undergo antigenic characterization. Subjects participating in the immunogenicity subset will have blood samples collected at their Days 1 and 22 clinic visit (for “previously vaccinated” subjects), or Days 1, 29 and 50 clinic visit (for “not previously vaccinated” subjects).
 
Subjects will be asked to return their completed Subject Diary at their Day 22 clinic visit (“previously vaccinated” subjects), or Day 29 and Day 50 clinic visit (“not previously vaccinated” subjects).
 
If a subject withdraws from the study, they will be asked to undergo a final assessment for safety.
		
Study Vaccines: Study Vaccine: QIVc A dose of 0.5 mL of QIVc contains purified viral envelope-glycoprotein hemagglutinin (HA) of each of the four (4) influenza strains recommended by WHO for inclusion in the quadrivalent vaccine composition for the influenza season corresponding to the year of the conduct of study. Comparator Vaccine: A dose of 0.5 mL of meningococcal (Groups A, C, Y, W-135) Conjugate Vaccine (Men ACWY) will be administered as non-influenza comparator vaccine.		
Efficacy Endpoints: Primary and Co-Primary Efficacy Endpoint: The primary and co-primary efficacy endpoint is the time from the last study vaccination to the onset of the first occurrence confirmed influenza by either RT-PCR-		

Name of Sponsor: Seqirus UK Ltd	Protocol number: V130_12	Generic name of study vaccine(s): Cell-Based Quadrivalent Subunit Influenza Virus Vaccine (QIVc) Meningococcal (Groups A, C, Y, W-135) Conjugate Vaccine (Men ACWY)
---	------------------------------------	--

confirmed or culture-confirmed (time to event analyses), due to any influenza Type A or B strain regardless of antigenic match to the strains selected for the seasonal vaccine, occurring at >14 days after the last vaccination and until the end of the influenza season

Secondary Efficacy Endpoint:

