Subjects who show clinical signs of influenza (see ILI case definition) will have an unscheduled visit in order to have a nasopharyngeal (NP) swab (or oropharyngeal swab if collection of NP swab is not feasible) collected for evaluation of the presence of influenza virus, and a safety follow-up call 30 days after ILI onset to determine if subsequent medically-attended adverse events occurred and concomitant medication associated with these events were used. The NP swab should be collected as soon as possible, within 3 days, and up to 6 days following onset of protocol defined ILI symptoms. In case ILI symptoms are present during a scheduled clinic visit, then the NP swab may be collected at this visit. NP swabs will be evaluated by RT-PCR and culture at a central laboratory, followed by characterization of the influenza strains as “vaccine strains” versus other influenza strains. RT-PCR and culture confirmed influenza cases will be evaluated within specific timeframes of first and second study vaccination (i.e., starting 14 days after study vaccination for “previously vaccinated” subjects and starting 14 days after second study vaccination for “not previously vaccinated” subjects). The evaluation for RT-PCR and culture influenza cases will end at the end of influenza season.

Total length of subject participation is until 180 days after last vaccination, or until the end of influenza season, whichever is longer.

This study is planned for multiple influenza seasons. Laboratory confirmed influenza cases will be reviewed on a regular basis (blinded review). Following the end of the second influenza season, and after observing at least 50% of planned events meeting the co-primary endpoint, an interim analysis for efficacy and futility will be performed by a DMC.

If the number of influenza cases is less or equal to 190 (minimum number of cases to

indicate efficacy or futility), no interim analysis for efficacy and futility will be done and the study will be extended.

If the number of influenza cases is greater or equal to 191 but less than 381 an interim analysis for efficacy and futility with an appropriate adjustment of the type I error will be conducted by an DMC, to decide if study objectives have been reached or the study may be extended. The need for further interim analyses and further extensions will be assessed by the DMC. If it is determined that the study objectives have been reached, enrolment will be halted.

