3.2 Study Period

Each subject should expect to participate in the study for 180 days after last vaccination, or until the end of the influenza season, whichever is longer (i.e. from the time of enrolment through the last study visit).

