8.1.1.2 Primary Efficacy Endpoint(s)

The primary efficacy endpoint is the time from the last study vaccination to the onset of the first occurrence confirmed influenza by either RT-PCR-confirmed or culture-confirmed, due to any influenza Type A or B strain regardless of antigenic match to the strains selected for the seasonal vaccine, occurring >14 days after the last vaccination and until the end of the influenza season.

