8.4.2.2 Analysis of Primary Efficacy Objective(s)

8.4.2.2.1 Statistical Hypotheses for Primary and Co-Primary Efficacy Objectives

The primary measure of efficacy is the estimate of absolute vaccine efficacy (aVE) of QIVc relative to the non-influenza comparator vaccine for preventing first-occurrence influenza-confirmed disease by either RT-PCR-confirmed or culture-confirmed influenza strains contained in QIVc and the non-influenza comparator, regardless of antigenic match.

Absolute vaccine efficacy (aVE) will only be assessed for laboratory confirmed influenza cases (by either RT-PCR-confirmed or culture-confirmed) with illness occurring at >14 days after the last vaccination and until end of the influenza season, since clinical protection is not immediate with vaccination.

Time-to-event methodology based on a proportional hazard model will be used for all efficacy analyses. Absolute vaccine efficacy (aVE) against first or only confirmed influenza cases will be determined using a standard formula: $aVE = 1 - HR$ where HR is the hazard ratio for influenza confirmed (by either RT-PCR-confirmed or culture-confirmed) ILI in the QIVc group versus the non-influenza comparator group. The HR will be estimated by a proportional hazards regression model, described in [Section 8.4.2.2.3](#). For which the following null (H_0) and alternative (H_1) hypotheses will be tested:

$$H_0: 1 - HR \leq 0.2 \text{ versus } H_1: 1 - HR > 0.2$$

where HR is a hazard ratio of QIVc versus non-influenza comparator and VE is vaccine efficacy. The primary objective will be achieved if the lower limit of the two-sided confidence interval of VE estimate, with at least 95% coverage in a multiple sequential hypothesis testing, exceeds 0.2 in subjects ≥ 2 years to <18 years of age.

The co-primary objective will be achieved if the lower limit of the two-sided confidence interval of VE estimate, with at least 95% coverage in a multiple sequential hypothesis testing, exceeds 0.3 in subjects ≥ 3 years to <18 years of age.

The co-primary objective will only be demonstrated in case of successful demonstration of the primary efficacy objective (i.e. in hierarchical testing procedure, only after demonstration of absolute vaccine efficacy of QIVc in subjects ≥ 2 years to <18 years of age).

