2.1.2 Primary and Co-Primary Endpoint

The primary and co-primary efficacy endpoint is the time from the last study vaccination to the onset of the first occurrence confirmed influenza by either RT-PCR-confirmed or culture-confirmed, due to any influenza Type A or B strain regardless of antigenic match to the strains selected for the seasonal vaccine, occurring > 14 days after the last vaccination and until the end of the influenza season.

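### SAP 11.1 lets the primary and co-primary case window run past the season end at which the defined endpoint stops, and the censoring text inherits the ambiguity (minor alignment)

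*SAP*

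**What the plan says.** **The outlier.** SAP 11.1, the section that specifies the confirmatory Cox model, evaluates efficacy on cases more than 14 days after the last dose and "until the end of study or the end of the influenza season, whichever is longer".

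**The endpoint.** SAP 2.1.2 stops at season end: "after the last vaccination and until the end of the influenza season". Protocol 8.1.1.2 agrees ("occurring >14 days after the last vaccination and until the end of the influenza season"), as do protocol 8.4.2.2.1 ("with illness occurring at >14 days after the last vaccination and until end of the influenza season") and the synopsis, both under the efficacy objectives ("days after last vaccination and until the end of the influenza season") and under the primary and co-primary endpoint ("occurring at >14 days after the last vaccination and until the end of the influenza season"). Protocol 3.1 is categorical: "The evaluation for RT-PCR and culture influenza cases will end at the end of influenza season".

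**The terms.** The protocol's Definitions and section 3.9 make end of study a study-level date: the completion of testing of the biological samples, no later than 8 months after LSLV. The Definitions put season end at the end of June (Northern Hemisphere, NH) or the end of December (Southern Hemisphere, SH). The longer-of-two construction does appear in protocol 3.2, but there it describes how long a subject should expect to "participate in the study for 180 days after last vaccination, or until the end of the influenza season, whichever is longer". That is participation, not the endpoint.

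**Censoring.** SAP 11.1 and protocol 8.4.2.2.4 right-censor subjects without an event in an observation period, and dropouts. Neither gives that period an end date.

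**The concern.** A programmer builds the analysis dataset from SAP 11.1. Followed literally, that section can count a confirmed case that SAP 2.1.2 excludes, and nothing in either document says which text prevails. Such a case would enter the Cox estimate and also the unadjusted estimate of vaccine efficacy (VE) from attack rates in the same section.

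What is at stake is a single reading of the confirmatory case window and censoring date before unblinding. If the choice is left open, it could be made with results in view.

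**Working it through.** **1. Two readings of end of study.**
- *As the protocol defines it* (sample testing complete, up to 8 months after LSLV): one date for the whole trial. SAP section 3 plans at least three seasons, so for a subject enrolled in an earlier season the window would run through later seasons. It cannot work as a subject's case window.
- *As the subject's own end of participation* (protocol 3.2: the later of 180 days after the last dose and season end): the window passes season end when last dose + 180 days falls after it.

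**2. Dates under the second reading** (non-leap year).
- NH: 1 January + 180 days = 30 June, so later last doses pass season end. A last dose on 1 February ends on 31 July (31 days over); one on 1 March ends on 28 August (59 days over).
- SH: 4 July + 180 days = 31 December.
- Protocol Tables 4 and 6 allow the final call from 7 days early to 14 days late. Taking 14 days off moves the thresholds to about 18 December (NH) and 20 June (SH). Where season end is the later anchor, the call may itself fall up to 14 days after it.

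The documents give no distribution of vaccination dates, so the share of subjects affected cannot be computed.

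**3. Can a post-season case be recorded at all?** The protocol is mixed.

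| Points to yes | Points to no |
|---|---|
| 5.3.2: a late safety call can lead to a site visit and swab | Definitions and 3.9: swabs may be collected up to season end |
| 5.5: a recent influenza-like illness (ILI) at the termination call leads to a swab | Synopsis, study procedures: families are asked to notify ILI onset until season end |
| 7.2: ILI is evaluated through study termination | 5.3.3: weekly calls stop at season end |

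Post-season cases are therefore possible, but they would be found without weekly surveillance.

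**4. The plan's own event targets.** Schoenfeld formula, D = 4(1.960 + 1.282)² / [ln(HR₁/HR₀)]², 1:1 allocation, 90% power:
- Co-primary: ln(0.50/0.70) = −0.3365, D = 372, against 381 stated.
- Primary: ln(0.55/0.80) = −0.3747, D = 300, against 298 stated.

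Both agree within 3%. This point does not dispute them.

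**5. Illustration of size.** Assumptions, not in the documents: a share q of the 381 cases is post-season, and VE is 0% there. In-season VE is 50%, so in-season cases split 1:2 and post-season cases 1:1. SE(log HR) = √(1/v + 1/c), where v and c are cases on vaccine and comparator. VE lower limit = 1 − HR·exp(1.96·SE).

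| q | v | c | VE | 95% lower limit |
|---|---|---|---|---|
| 0% | 127.0 | 254.0 | 50.0% | 38.1% |
| 1% (3.8 cases) | 127.6 | 253.4 | 49.6% | 37.7% |
| 5% (19.1 cases) | 130.2 | 250.8 | 48.1% | 35.9% |

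All three limits are above the 30% criterion. If VE after season end were also 50%, the estimate would not move.

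**The case against.** The case for leaving this as editorial is strong. One phrase stands against at least six consistent statements, SAP 2.1.2 defines the endpoint correctly, and few if any swabs may be taken after season end.

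Extra event-free time adds little of its own. In a Cox model it acts only through membership of risk sets, and the same rule extends both randomised arms. Because time runs from last vaccination, a subject dosed on 1 February reaches day 160 on 11 July. That subject could sit in the risk set for a day-160 case in someone dosed on 15 October, which falls on 24 March. Randomisation should balance this between arms, so it is an unspecified risk set and not evidence of bias.

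A reader might also infer a second, separate defect in the censoring rule. The documents do not support that: the observation period sits in the same section as the case window and naturally refers to it, so its end is unclear only because the window's end is.

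These arguments set the severity. They do not remove the conflict, because the deviating phrase is in the section that governs the analysis and no clause ranks it below the endpoint definition.

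**Conclusion.** The conflict holds as a minor misalignment of the confirmatory case window. Read literally, SAP 11.1 can admit cases outside the endpoint that the SAP and protocol define. Their number is unknown and probably small.

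A reader might infer that efficacy will be diluted, power lost or success put at risk. On the 5% illustration, power at 381 events would be 83% instead of 90.7%. That rests entirely on an assumed case share and an assumed VE of 0%, and the documents give neither. No change in power or conclusion is claimed.

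A reader might also think season end is undefined for tropical sites. The protocol's Definitions assign them to an NH or SH season by vaccine formulation and timing of vaccination, so this is not a gap to press.

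**What to change.** Before unblinding, in SAP 11.1:

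1. Replace "until the end of study or the end of the influenza season, whichever is longer" with *until the end of the influenza season (protocol definition)*, which matches SAP 2.1.2.
2. State that a subject without a confirmed influenza event is censored at the earlier of (a) the end of the influenza season in which the subject was enrolled and (b) dropout or last contact.
3. If a data cut-off is used for censoring, limit it to the interim analysis itself. As a general rule it would also discard valid in-season follow-up from the final analysis.

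The cost is one phrase and a short censoring statement. No new data are needed, and the event targets of 298 and 381 are unchanged.
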